8.3.1.2 Sensitivity Analysis of the Primary Efficacy Variable

If pre-dose assessment is missing and the post-dose assessment is available on Day 15, the missing record will be imputed by post-dose assessment on the same day. The sensitivity analysis of the change from baseline in ppFEV₁ is performed on the imputed data. The sensitivity analysis will be based on an MMRM model, similar to the primary analysis of the primary efficacy variable in Parts D, E and F. The tabular presentation of results will also be similar. The adjusted mean and 95% CI of the mean change from baseline of the average treatment effect through Day 29 will be provided along with *p*-value for all within-treatment and between-treatment comparisons, for each part, separately.

8.3.1.3 Supportive Analysis for the Primary Efficacy Variable

8.3.1.3.1 Part D: Period 2

Period 2 in Part D (after Day 29 through the Period 2 visit) will be used to assess the washout effect of VX-445 on the primary efficacy variable during the 1-week Period 2. This analysis will be based on fitting an Analysis of Covariance (ANCOVA) model to the primary efficacy variable in the Period 2, using the group as a fixed effect, and continuous baseline ppFEV₁ as a covariate in the ANCOVA model. Group will be assigned to placebo, TC-low, pooled TC-mid, and TC-high the 4 randomized groups in the Period 1.

The adjusted mean and 95% CI of the mean change from baseline for placebo, TC-low, pooled TC-mid, and TC-high at the Period 2 visit will be provided along with the corresponding 95% CI and *p*-value. The adjusted mean (with 95% CI) obtained from the ANCOVA analysis at Period 2 visit will be plotted by randomized group, and will be combined with the corresponding plot for the Period 1 from the primary efficacy analysis.

8.3.1.3.2 Part E: Washout Period

The Washout Period in Part E after Day 29 through Day 57 will be used to assess the washout effect of VX-445 on the primary efficacy variable during the 4-week Washout Period. This analysis will be based on fitting a fully saturated model to the primary efficacy variable in the Washout Period, using group, visit and the group-by-visit interaction effect as a fixed effect, and continuous baseline ppFEV₁ as a covariate in the MMRM model. Group (1 versus 2) will be assigned to the two randomized groups in the Period 1, and visit will be assigned the chronological visit within each subject. The other aspects of the MMRM model will be similar to that of the primary analysis.

The adjusted mean of the mean change from baseline for TC and TEZ/IVA at the Washout Period visits Day 43, and Day 57 will be provided along with the corresponding 95% CI and *p*-value. Contrasts based on the fixed effects in the model defined at the baseline covariate mean for the combined treatment groups using unique subjects in the FAS who have at least one post-baseline measurement in the Washout Period, will be used to estimate the adjusted mean at each visit in the Washout Period.

The adjusted mean (with 95% CI) obtained from the MMRM analysis at each post-baseline visit post Day 29 of the Period 1 through Day 57 of the Washout Period will be plotted by randomized

group, and combined with the corresponding plot for the Period 1 from the primary efficacy analysis.

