9.1.2.5 Washout Period (Part E)

The Washout Period of Part E will last approximately 4 weeks and is designed to evaluate the effect on PD and efficacy endpoints as subjects step down from TC to TEZ/IVA. Subjects will receive TEZ 100 mg qd/ IVA 150 mg q12h during the Washout Period.

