12.3.3 Efficacy Analysis (Parts D, E, and F Only)

12.3.3.1 Analysis of Primary Variables

The primary efficacy variable is the absolute change from baseline for ppFEV₁ through Day 29 in Parts D, E, and F. The analysis will be performed using a mixed-effects model for repeated measures (MMRM) with change from baseline as the dependent variable. The model will include treatment group, visit, and treatment-by-visit interaction as fixed effects, subject as random effect, and the continuous baseline ppFEV₁ as a covariate. The model will be estimated using restricted maximum likelihood. Denominator degrees of freedom for the F test for fixed effects will be estimated using the Kenward-Roger approximation. An unstructured covariance structure will be used to model the within-subject errors. If the model estimation does not converge, a compound symmetry covariance structure will be used. Conditional on observed data and covariates, missing data due to treatment or study discontinuation will be assumed to be missing at random.

Adjusted means and 95% confidence intervals of the average treatment effects through Day 29, as applicable, with 2-sided *P* values, will be estimated within MMRM using LSMeans via PROC MIXED in SAS, for all within-group and between-group comparisons in both parts.

Sensitivity analyses for handling missing data due to treatment or study discontinuation will be described in the SAP.

Additional supportive analyses utilizing the Washout Period in Part E to compare treatment groups will be described in the SAP. Subgroup analyses will also be described in the SAP.

There will be no multiplicity adjustment for performing multiple hypothesis tests.

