The adjusted means and 95% confidence intervals (CI) of the average treatment effect through Day 29 (Day 15 and Day 29 only) for each triple combination, with a 2-sided *p*-value will be estimated within MMRM using PROC MIXED in SAS, for all within-treatment and between-treatment comparisons, for each part, separately. Contrasts based on the fixed effects in the model, defined at the baseline covariate mean for the combined treatment groups using unique subjects in the FAS who have at least one post-baseline measurement through Day 29, will be used to estimate the average treatment effect across post-baseline visits through Day 29. Day 8 data will not be included in the model for the through Day 29 analysis for Part D.

Further, the adjusted mean and 95% CI of the treatment difference between each triple combination and placebo or TEZ/IVA at each post-baseline visit through Day 29 will be provided along with the corresponding *p*-value, for each part. In addition, the adjusted mean and 95% CI of the within-treatment difference at each post-baseline visit through Day 29 for each treatment group will be provided along with the *p*-value, for each part.

The adjusted mean (with 95% CI) obtained from the MMRM analysis at each post-baseline visit through Day 29 will be plotted by treatment group, for each part. In addition, a waterfall plot showing the subject-level absolute change in ppFEV₁ at Day 29 will be presented, by treatment group.

In addition, for each part, descriptive analyses of the change from baseline will be performed using pre-dose records for all treatment groups by post-baseline visit through the safety follow-up visit.

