8.3.5.2.1 Parts D, E and F

The analysis of the absolute change in sweat chloride from baseline through Day 29 will be based on an MMRM model similar to the analysis of the primary efficacy variable for Parts D, E, and F, with the continuous baseline sweat chloride and continuous baseline ppFEV₁ as covariates. The presentation of results will also be similar.

The adjusted mean (with 95% CI) obtained from the MMRM analysis at each post-baseline visit through Day 29 in the Period 1 will be plotted by treatment group, for each part.

A waterfall plot showing the subject-level absolute change in sweat chloride at Day 29 will be presented, by treatment group for each part.

In addition, for each part, descriptive analyses of the change from baseline will be performed for all treatment groups by post-baseline visit.

8.3.5.3 Supportive Analysis for Absolute Change from Baseline in Sweat Chloride from Baseline through Day 29

Part D: Period 2

The Period 2 in Part D after Day 29 through Period 2 visit will be used to assess the washout effect of VX-445 on sweat chloride during the 1-week Period 2. This analysis will be based on fitting an Analysis of Covariance (ANCOVA) model to the absolute change from baseline in sweat chloride in the Period 2, using the group as a fixed effect, with the continuous baseline sweat chloride and baseline ppFEV₁ as covariates in the ANCOVA model. Groups will be assigned to placebo, TC-low, pooled TC-mid and TC-high the 4 randomized groups in the Period 1, will be assigned within each subject.

The adjusted mean of the change from baseline for placebo, TC-low, pooled TC-mid and TC-high at the Period 2 visit will be provided along with the corresponding *p*-value.

The adjusted mean (with 95% CI) obtained from the ANCOVA analysis at Period 2 visit will be plotted by randomized group, will be combined with the corresponding plot for the Period 1 from the primary analysis of sweat chloride.

Part E: Washout Period

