The Washout Period in Part E after Day 29 through Day 57 will be used to assess the washout effect of VX-445 on sweat chloride during the 4-week Washout Period. This analysis will be based on fitting a fully saturated model to the absolute change from baseline in sweat chloride in the Washout Period, using the group, visit, and group-by-visit interaction effect as a fixed effect, with the continuous baseline sweat chloride and baseline ppFEV₁ as covariates in the MMRM model. Group (1 versus 2) will be assigned to the two randomized groups in the Treatment Period, and visit will be assigned the chronological visit within each subject. The other aspects of the MMRM model will be similar to that of the primary analysis.

The adjusted mean and 95% CI of the mean change from baseline for TC and TEZ/IVA at the Washout Period visits Day 43 and Day 57 will be provided along with the corresponding *p*-value. Contrasts based on the fixed effects at the covariate mean of the continuous baseline sweat chloride and baseline ppFEV₁ for the combined treatment groups based on unique subjects in the FAS who have at least one post-baseline measurement in the Washout Period, will be used to estimate the adjusted mean at each visit in the Washout Period.

The adjusted mean (with 95% CI) obtained from the MMRM analysis at each post-baseline visit in the Washout Period will be plotted by group, combined with the corresponding plot for the Period 1 from the primary analysis of sweat chloride.

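### Part E Washout: the protocol announces a treatment-group comparison, but the SAP specifies no TC-high minus TEZ/IVA difference for ppFEV1 at Day 43 or Day 57 (sweat chloride has the same gap)

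*SAP*

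**What the plan says.** Protocol 12.3.3.1, on the primary variable (ppFEV1), states: "Additional supportive analyses utilizing the Washout Period in Part E to compare treatment groups will be described in the SAP". Protocol 9.1.2.5 describes the Washout Period as "designed to evaluate the effect on PD and efficacy endpoints as subjects step down from TC to TEZ/IVA". In Part E, 18 subjects are planned for TC-high and 6 for placebo + TEZ/IVA. VX-445 or its placebo stops at Day 29, and both arms continue TEZ/IVA to Day 57.

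For ppFEV1, SAP 8.3.1.3.2 says the period will be used to assess the washout effect of VX-445. It fits an MMRM "using group, visit and the group-by-visit interaction effect as a fixed effect", with baseline ppFEV1 as covariate. The specified output is "The adjusted mean of the mean change from baseline for TC and TEZ/IVA at the Washout Period visits Day 43, and Day 57", with the corresponding 95% CI and p-value. The contrasts "will be used to estimate the adjusted mean at each visit in the Washout Period". A plot by randomised group is added.

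For sweat chloride, the Part E section of SAP 8.3.5.3 follows the same pattern: "The adjusted mean and 95% CI of the mean change from baseline for TC and TEZ/IVA at the Washout Period visits Day 43". The same is given for the Day 57 visit, in each case with a p-value.

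Through Day 29, by contrast, SAP 8.3.1.1.1 asks explicitly for "the adjusted mean and 95% CI of the treatment difference between each triple combination and placebo or TEZ/IVA at each post-baseline visit", and lists the within-treatment change separately.

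**The concern.** The protocol left it to the SAP to describe a Washout comparison of treatment groups, and for ppFEV1 the SAP does not specify one. The p-value attached to an arm's adjusted mean change asks whether that arm differs from its own Day 1 baseline. That is a different question from whether the arm that took VX-445 differs from the arm that did not.

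Followed as written, a statement about residual VX-445 effect at Day 43 or Day 57 would rest on the TC-high arm's change alone, or on an informal reading of two separate tests. The first counts any change common to both arms as VX-445 effect, or lets such a change hide one. The second is unreliable with 18 and 6 subjects. At a common SD the standard error of the control mean is √(18/6) ≈ 1.73 times that of TC-high, so one arm can be significant and the other not without any difference between them.

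**Working it through.** **1. Is the difference specified somewhere else?** The relevant SAP sections, side by side:

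| SAP section | Period | Between-arm output |
|---|---|---|
| 8.3.1.1.1, ppFEV1 primary | through Day 29 | Named explicitly, apart from the within-arm change |
| 8.3.1.2, ppFEV1 sensitivity | through Day 29 | Within- and between-treatment comparisons both requested |
| 8.3.5.2.1, sweat chloride | through Day 29 | Presentation to be similar to the primary variable |
| 8.3.1.3.2, ppFEV1 Washout | Day 43, Day 57 | None; per-arm adjusted means only |
| 8.3.5.3, sweat chloride Washout | Day 43, Day 57 | None; per-arm adjusted means only |
| 8.3.2.2, CFQ-R Washout | Day 57 | Arguable: ANCOVA on randomised group, tables similar to the primary analysis |

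The ppFEV1 and sweat chloride Washout sections do say that other aspects of the MMRM will resemble the primary analysis. That carries over the model, not the list of estimates, and neither section has a clause carrying over the presentation of results. SAP 2.1 lists two modifications to the protocol: the treatment-emergent definition and an added ppFEV1 sensitivity analysis. Omitting the Washout comparison is not among them.

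**2. What does each quantity estimate?** At a given Washout visit, let r be the residual VX-445 effect in TC-high and s the mean change from Day 1 common to both arms.

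- Expected change in TC-high: r + s
- Expected change in TEZ/IVA: s
- Difference: (r + s) − s = r

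The planned TC-high p-value tests r + s = 0. It tests r = 0 only if s = 0. The documents give no figure for s.

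**3. Can the planned model estimate the difference?** Yes. Group, visit and group-by-visit terms are all in it, so the difference at each visit is one linear contrast.

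**4. How precise would it be?** The documents give no SD. One bound comes from the sizing statement in SAP 6.2.1.1 (18 subjects, 7 points, at least 90% power). Read as a two-sided 5% one-sample t-test, it requires an SD of at most 8.63. I take 5, 7 and 8.6 as assumed values, with a common SD, no covariate adjustment and no missing data.

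- Difference, 18 v 6: half-width = t(0.975, 22) × SD × √(1/18 + 1/6) = 2.074 × 0.471 × SD
- TC-high mean alone: half-width = t(0.975, 17) × SD / √18 = 2.110 × SD / 4.243

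| Assumed SD | Difference, ± points | TC-high own mean, ± points |
|---|---|---|
| 5 | 4.9 | 2.5 |
| 7 | 6.8 | 3.5 |
| 8.6 | 8.4 | 4.3 |

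The two columns describe different quantities, r and r + s. Each interval is valid for its own target. The table shows only how wide the added result would be.

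**The case against.** The best defence is that within-arm change is this study's declared framework. The primary null hypothesis in SAP 8.3.1.1.1 is within-group, and the Part E run-in exists to establish a stable baseline on TEZ/IVA (Protocol 9.1.2.3). Whether TC-high subjects return to that baseline is a sensible question, and per-arm change answers it. Common drift may also be small: Protocol 9.3.2.2 reports that in earlier studies most of the effect appeared within 14 days, and baseline follows four weeks of TEZ/IVA. The analyses are supportive, no decision rule uses them, and an 18 v 6 contrast is imprecise.

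Most of this stands, and it keeps the point modest. It justifies retaining the per-arm means. It does not explain why a comparison announced in the protocol is missing, and imprecision is a reason to show the wide interval rather than leave it out.

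Three stronger readings are tempting, and the documents do not support them.

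- *The randomised arms are not compared at all after Day 29.* The adjusted means are plotted by group, SAP 8.3.1.1.1 gives descriptive ppFEV1 changes by treatment group through safety follow-up, and the CFQ-R ANCOVA at Day 57 arguably yields a between-arm result.
- *The protocol commitment is broken for sweat chloride too.* The sentence sits under the primary variable. Protocol 12.3.4 leaves further sweat chloride detail to the SAP and mentions no Washout comparison.
- *Part D Period 2 has the same defect.* SAP 8.3.5.3 there gives "The adjusted mean of the change from baseline for placebo, TC-low, pooled TC-mid and TC-high at the Period 2 visit will be provided", again per group. But the protocol promises no comparison for that period, and a contrast with placebo would also contain any TEZ/IVA effect, because placebo subjects take dual placebo.

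**Conclusion.** The point holds for Part E ppFEV1. The protocol says the Washout Period will be used to compare treatment groups; the SAP specifies no between-arm estimate, interval or p-value at Day 43 or Day 57 and does not record the departure. Sweat chloride has a parallel omission, not a broken commitment. This is a should-fix item in a supportive analysis and leaves the primary analysis through Day 29 untouched.

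The size of any misreading cannot be stated, because it depends on a common change s for which the documents give no figure; the run-in design suggests it may be small. The argument that the difference is the right target rests on both arms taking the same TEZ/IVA regimen after Day 29, which the documents do state. The precision figures rest on the assumed SDs and full follow-up.

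**What to change.** In SAP 8.3.1.3.2 and in the Part E section of 8.3.5.3, add that the adjusted mean difference between TC-high and TEZ/IVA in change from baseline at Day 43 and at Day 57, with 95% CI and p-value, will be estimated from the same MMRM, and that statements about residual VX-445 effect will be based on it. Keep the per-arm means and plots. If the sponsor prefers not to make the ppFEV1 comparison, list that in SAP 2.1 as a modification to the protocol.

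The cost is one sentence per section and one estimate per visit from models already planned; no new data or subjects are needed. The downside is a wide interval, roughly ±4.9 to ±8.4 ppFEV1 points under the assumptions above, so the supportive result will look imprecise.

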8.3.2 Analysis of Secondary Efficacy Variables

The secondary efficacy variables include:

- Relative change in ppFEV₁ from baseline through Day 29
- Absolute change in Cystic Fibrosis Questionnaire-Revised (CFQ-R) respiratory domain score from baseline at Day 29

8.3.2.1 Relative change in ppFEV₁ from baseline through Day 29 (Parts D , E and F)

The relative change in ppFEV₁ from baseline through Day 29 is defined in [Section 8.1](#). Analysis of this variable will be based on an MMRM model, similar to the primary analysis of the primary efficacy variable in Parts D, E and F. The tabular presentation of results will also be similar.

8.3.2.2 Absolute change in the CFQ-R respiratory domain score from baseline at Day 29 (Parts D, E and F)

The absolute change in the CFQ-R respiratory domain score from baseline at Day 29 will use the 'Adolescents and Adults' Version for ages 14 and above at baseline, and will be based on the *CFQ-R scaled scores*, as described in [Appendix F](#). Analysis of this variable will be based on an MMRM model, similar to the analysis of the primary efficacy variable in Parts D, E and F. Sex, the continuous baseline ppFEV₁, and the continuous baseline CFQ-R respiratory domain score will be used as covariates in Parts D, E and F. The presentation of results will also be similar.

Part E: Washout Period

In Part E, a supportive analysis will be based on fitting an ANCOVA model to the CFQ-R respiratory domain score Day 57 Visit during Washout Period, using the randomized group in Period 1, as a fixed effect. Sex, continuous baseline ppFEV₁, and continuous baseline CFQ-R respiratory domain score will be used as covariates.

The tabular presentation of results for the average treatment effect across visits will be similar to the primary analysis of the primary efficacy variable for all parts. The adjusted mean (with 95% CI) obtained from the model-based analysis at each post-baseline visit will be plotted by randomized group for each part.

In addition, a waterfall plot showing the subject-level absolute change in CFQ-R at Day 29 will be presented, by treatment group, for each part.

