7.2 Secondary Endpoints

Parts A and B: PK parameter estimates of VX-445 derived from plasma concentration-time data

[figure not shown]
Part C:

- PK parameter estimates of VX-445 derived from plasma concentration-time data
- PK parameter estimates for TEZ and metabolites (M1-TEZ and M2-TEZ), and IVA and metabolites (M1-IVA and M6-IVA) derived from plasma concentration-time data

Parts D and E:

- Absolute change in sweat chloride concentrations from baseline through Day 29
- Relative change in ppFEV₁ from baseline through Day 29
- Absolute change in Cystic Fibrosis Questionnaire-Revised (CFQ-R) respiratory domain score from baseline at Day 29
- PK parameters of VX-445, TEZ, M1-TEZ, IVA, and M1-IVA

Part F:

- Absolute change in sweat chloride concentrations from baseline through Day 29
 - Relative change in ppFEV₁ from baseline through Day 29
 - Absolute change in CFQ-R respiratory domain score from baseline at Day 29
 - PK parameters of VX-445, TEZ, M1-TEZ, and VX-561
- 

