5.1.2 Secondary Efficacy Endpoints

Parts D and E:

- Absolute change in sweat chloride concentrations from baseline through Day 29
- Relative change in ppFEV₁ from baseline through Day 29
- Absolute change in Cystic Fibrosis Questionnaire-Revised (CFQ-R) respiratory domain score from baseline at Day 29
- PK parameters of VX-445, TEZ, M1-TEZ, IVA, and M1-IVA

Part F:

- Absolute change in sweat chloride concentrations from baseline through Day 29
- Relative change in ppFEV₁ from baseline through Day 29
- Absolute change in CFQ-R respiratory domain score from baseline at Day 29
- PK parameters of VX-445, TEZ, M1-TEZ, and VX-561

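### The CFQ-R respiratory endpoint is change at Day 29, but the only contrast SAP 8.3.2.2 names for its table is the average over Day 15 and Day 29, and no contrast is identified as the endpoint result

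*SAP*

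**What the plan says.** Both documents place the endpoint at one visit. Protocol 7.2 lists "Absolute change in Cystic Fibrosis Questionnaire-Revised (CFQ-R) respiratory domain score from baseline at Day 29", and SAP 5.1.2 repeats it for Part F as "Absolute change in CFQ-R respiratory domain score from baseline at Day 29". In the same lists sweat chloride and ppFEV₁ are defined over a span, as in "Relative change in ppFEV₁ from baseline through Day 29". The distinction between *at* and *through* is kept consistently in the protocol and the SAP, including the heading of SAP 8.3.2.2.

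SAP 8.3.2.2 analyses CFQ-R with an MMRM modelled on the primary analysis, with sex, baseline ppFEV₁ and baseline CFQ-R score as covariates. It then makes two statements about reporting:

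- After the model description: "The presentation of results will also be similar".
- After the Part E washout paragraph: "The tabular presentation of results for the average treatment effect across visits will be similar to the primary analysis". This second sentence is stated to cover every part.

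The section also plans a by-visit plot of adjusted means with 95% CIs and a Day 29 waterfall plot.

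The primary analysis in SAP 8.3.1.1.1 reports the "average treatment effect through Day 29 (Day 15 and Day 29 only) for each triple combination". It further reports the within-group change and the between-group difference at every post-baseline visit, each with a 95% CI and p-value.

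**The concern.** An endpoint fixed at one visit should have one identified estimate, taken at that visit. Here the only contrast that the section names for a table is a two-visit average. That wording suits the ppFEV₁ endpoints. It also suits sweat chloride, where SAP 8.3.5.1 uses a near-identical sentence for an endpoint that does run through Day 29. In 8.3.2.2 it appears not to have been adapted.

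A programmer or report writer who follows the sentence literally could place the average in a table titled as the Day 29 endpoint. The by-visit output would hold a second estimate and p-value for the same comparison, with no rule for choosing between them. SAP 8.3.2.3 applies no multiplicity adjustment to secondary variables. SAP section 3 says this plan also governs the interim analyses and is to be final before the first interim data cut, and SAP 9.1 gives a limited sponsor team sight of the interim results. The choice should therefore be settled in the text and not at reporting.

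**Working it through.** **Step 1. Set the texts side by side.**

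| Item | Time reference | Place |
|---|---|---|
| CFQ-R respiratory endpoint | Day 29 only | Protocol 7.2; SAP 5.1.2; heading of SAP 8.3.2.2 |
| Contrast named for the CFQ-R table | Average across visits | SAP 8.3.2.2 |
| Visits in that average | Day 15 and Day 29 | SAP 8.3.1.1.1 |
| By-visit estimates, CIs, p-values | Each visit, so including Day 29 | SAP 8.3.1.1.1, carried over by 8.3.2.2 |

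CFQ-R is collected on Days 1, 15 and 29 in Parts D, E and F (also Day 57 in Part E), so one fitted model gives both contrasts. The table sentence sits below the Part E washout heading, but it refers to all parts, so its position does not confine it to the washout. Protocol 12.3.3.2 does not settle the matter: it calls the secondary analysis similar to the primary one and leaves the details to the SAP.

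**Step 2. Is there a figure to reproduce?** No. The documents give no SD, correlation, effect size or power for CFQ-R. The stated power (18 subjects per group, a change of 7 points) concerns ppFEV₁. What follows is illustration under assumed values.

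**Step 3. Point estimate.** Let E15 and E29 be the effects at the two visits.

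Average − E29 = (E15 + E29)/2 − E29 = (E15 − E29)/2.

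If E15 = k × E29, the average is (1 + k)/2 of E29:

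- k = 1.0: 1.00
- k = 0.8: 0.90
- k = 0.7: 0.85
- k = 0.5: 0.75

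**Step 4. Standard error.** Assume equal variance σ² at both visits, correlation ρ between the adjusted changes, and complete data.

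Var(average) = (σ² + σ² + 2ρσ²)/4 = σ²(1 + ρ)/2, so SE(average)/SE(Day 29) = √((1 + ρ)/2).

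- ρ = 0.5: √0.75 = 0.866
- ρ = 0.7: √0.85 = 0.922
- ρ = 0.8: √0.90 = 0.949

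Apart from small differences in degrees of freedom, CI widths scale the same way. The average's interval is then about 5% to 13% narrower than the Day 29 interval.

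**Step 5. Test statistic.** The ratio of the average's statistic to the Day 29 statistic is [(1 + k)/2] / √((1 + ρ)/2).

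| k | ρ = 0.5 | ρ = 0.7 | ρ = 0.8 |
|---|---|---|---|
| 1.0 | 1/0.866 = 1.15 | 1/0.922 = 1.08 | 1/0.949 = 1.05 |
| 0.7 | 0.85/0.866 = 0.98 | 0.85/0.922 = 0.92 | 0.85/0.949 = 0.90 |

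The average gives the smaller p-value only if k exceeds 2√((1 + ρ)/2) − 1, which is 0.73, 0.84 and 0.90 at the three correlations. The direction depends on a time course that the documents do not give.

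**The case against.** The strongest reply is that the Day 29 result is already planned. The carry-over sentence in 8.3.2.2 brings across the by-visit differences and within-group changes of the primary analysis, with CIs and p-values, and a by-visit plot and a Day 29 waterfall plot are added. Since the section heading and the endpoint lists all say Day 29, a reader could naturally take the Day 29 estimate as the answer and the average as an extra. CFQ-R also has no stated power or decision rule.

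Most of this stands, and it rules out two stronger readings. A reader might infer that the SAP replaces the Day 29 endpoint with the average, or makes the average its main result. No text says so, and the Day 29 contrast is produced. A reader might also infer that the average flatters the evidence through a smaller p-value. Step 5 shows that this fails whenever the Day 15 effect is sufficiently below the Day 29 effect: at 70%, the p-value is larger at all three correlations.

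What the reply does not remove is the mismatch in the stated text. The contrast expressly named for the table, for every part, is not the endpoint, and the one that matches is reached only through a general cross-reference and is not labelled.

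**Conclusion.** The point holds as a conflict between the endpoint definition and the one contrast named for its table, together with a missing statement of which contrast reports the endpoint. It does not show that the endpoint's own estimate is lost or that the result would be biased in a known direction.

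If the average were reported as the endpoint, the estimate would be off by half the Day 15 to Day 29 difference in effect, and by zero if the effect is flat. The interval would be about 5% to 13% too narrow for a Day 29 quantity at assumed correlations of 0.8 to 0.5, given equal variances and complete data. None of these inputs is in the documents, so the actual gap cannot be computed from them.

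**What to change.** In SAP 8.3.2.2, replace the table sentence with wording such as: *The Day 29 within-group and between-group contrasts from the MMRM, with 95% CI and p-value, are the result for the CFQ-R respiratory domain secondary endpoint in each part; the average over Day 15 and Day 29 is supportive.* Make the change before the first interim data cut.

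The cost is one sentence. Both contrasts come from the same fitted model, and no new data or analysis is needed. The downside is that the interval reported for the endpoint is likely to be slightly wider than that of the average.
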